6.2 Exclusion Criteria

1. <18 years of age
2. Patients requiring treatment in supine position

6.3 Enrollment

The source of subjects is the patient population at the Banner – University Medical Center Tucson/Arizona Cancer Center. Patients who are scheduled as part of their routine care to consult with the radiation oncologist for treatment of left sided breast cancer will be provided with information regarding this study. See attached list for our website, newsletter and Front Desk Poster.

Subjects will be consented at an already scheduled appointment with the radiation oncologist. This could be either at their initial consult visit or prior to their CT simulation appointment. Subjects will have the opportunity to take their time in making a decision, and will be encouraged to take the Informed Consent Form home and discuss it with whomever they would like. The treating physician will explain to the subjects the risks and benefits. They will be informed that their participation is voluntary, and lack of participation will not affect the subject's relationship with the treating staff or our facility. Subjects will be consented by either the PI, Co –PI, or the Research Staff of the Radiation Oncology department. Subjects will also be made aware that should they consent, they can withdraw their consent at any time. When new information becomes available, it

will be given to the patient as soon as possible, either at their next visit, or if that is more than 30 days away, by phone call. Once an approved revised consent form is submitted and approved by the IRB, the subject will be asked to sign the new consent and the subject will be notified of the change to the consent form. The AZCC Verification of Consent form will be completed at the time the subject is consented. This form includes information pertaining to who is present at consenting, that the consent form was reviewed with the subject, the subject understood the consent form, and the date and the time of the consent. Also documented will be the version of the Subject Consent form and the HIPAA form. Only English speaking patients will be enrolled.

7. STUDY PLAN

7.1 Treatment Regimen

Subjects will be recruited by [name] and [name] (or covering physician) at their standard of care appointment prior to the radiation planning appointment. Patients will be asked by [name] and [name] (or covering physician) if they are interested in participating in the study. If they are, a member of the research staff will review the study with the patient and complete the consent process. Subjects will be enrolled prior to their radiation therapy panning simulation (CT simulation).

During the radiation planning appointment, patients undergo CT scans used to plan the radiation doses and delivery. The number of images taken during the CT simulation is the same as if they were not treated on this research study. A CT scan will be performed in the prone position using coached voluntary inspiratory breath-holding using the RPM visual feedback system. Prone breath hold will be conducted using a monitor in the headrest of the prone breastboard that the subject will watch. This monitor allows the subjects to see their respiratory cycle which is a sinusoidal curve. Therapists coach the patient to hold their breath for approximately 15 seconds in order to maintain inspiration within a threshold bar set by the simulation therapists that is seen via the patient monitor. The purpose of the breath hold technique is to allow for optimal heart positioning for this study. This is the same method used for breath hold in the supine position which is considered standard of care. The reason this study is unique is because it is using the combination of prone positioning and inspiratory gated breath hold versus individually.

After the subject completes the radiation planning simulation, the physician will generate two radiation treatment plans: one for the free-breathing scan (standard of care) and one for the breath-hold scan (using inspiratory gating). For each plan, the heart, left ventricle/LAD artery and lungs will be contoured on each CT scan with radiation fields placed on both CT scans to dosimetrically determine heart, left ventricle/LAD artery and lung radiation doses and coverage of the affected breast. The doses to the heart, left ventricle/LAD artery and lungs will be compared to determine the plan with the lower cardiac and lung doses.

At the discretion of the treating physician, the plan with the lower cardiac and lung doses will be used to treat the subject. Inspiratory breath hold will only be used if it results in lower cardiac and lung doses. If the free breathing plan shows

lower cardiac and lung doses, the patient will be treated per standard of care (prone without inspiratory breath hold). If the plan involves inspiratory breath hold, the subject will be notified by the research staff prior to the first day of treatment. Reasoning for treating a patient prone only versus prone and breath-hold will be documented by the treating physician. If the plan with inspiratory breath hold resulted in the lower cardiac and lung dose, inspiratory gating will be performed during each daily treatment. Treatment with breath hold adds approximately 5 minutes to the overall setup and treatment time of each daily treatment. During daily radiation, prone breath hold will be conducted using a monitor below the prone headrest that the patient will watch. This monitor allows the patient to see their respiratory cycle and indicates the amount of inhalation that would be required (threshold bar represented as a blue box) in order to allow for treatment that is representative each day of their initial simulation CT scan. This monitor allows the subjects to see their respiratory cycle which is somewhat of a sinusoidal curve. Therapists coach the patient to hold their breath for approximately 15 seconds in order to maintain inspiration within a threshold bar (blue box) set by the simulation therapists that is seen via the patient monitor. During treatment, the radiation beam is only active when the patient breath hold is within the threshold bar on the monitor. The radiation treatment machine is set to turn off when the breath hold is outside of this threshold bar (blue box).

The physician will complete an evaluation form (RTOG CF form attached) regarding cardiac co-morbidities. The form will be completed at baseline (radiation planning session) and at 6 months post RT, and then at 1 year. This will not require any additional time for the subject and will be based on the information gathered by the physician at the standard of care appointment.

In addition to the intervention, data from the subjects medical record will also be collected (please see attached data collection sheet). Details regarding the subject's treatment, imaging studies, medical history and follow up visits will be collected. The research staff has access to the medical record as part of their position with UA/UAMC.

7.2 Pre-medications:
Not Applicable

7.3 Rescue medications:
Not Applicable

7.4 Excluded medications:
Not Applicable

8. REQUIREMENTS FOR TREATMENT

8.1 Standard dose/treatment
Not applicable

8.2 Dose/treatment modification
Not applicable

- 8.3 Investigational Product Dose Delay
Not Applicable
- 8.4 Definition of a Dose Limiting Toxicity (DLT)
Not Applicable

9. STUDY PROCEDURES (the actual procedures need to be entered below and/or in a study schema/calendar – see my note in section # 26)

- 9.1 Screening
Potential subjects will enter the screening period of the study after completely executing a study specific informed consent form.
- 9.2 Registration/Randomization
Once this study is approved by all internal regulatory agencies to enroll subjects, study enrollment will begin. Subjects will be entered into the study. Subjects will be identified by their initials (First, Middle if available, Last) and a study number. Study numbers will begin with GO-B-001 and continue sequentially.
The subject CT Simulation will be scheduled.
- 9.3 On Intervention: Subjects will undergo the standard of care CT simulation, which includes an additional breath hold CT. Inspiratory gated breath-hold will be used. Two radiation plans will be generated: one for the CT scan performed free breathing, and one for the scan performed with inspiratory gated breath hold. The cardiac and lung doses will be determined. At the discretion of the treating physician, the plan with the lower cardiac and lung dose may be used to treat the patient.
- 9.4 End of Intervention: The intervention will be considered complete at the time the patient's treatment plan has been generated.
- 9.5 Follow up
Subjects will be seen for one 30 day [± 10 days] follow-up visit after the end of RT then at 6 months (± 30 days) and then at one year (± 30 days) from the end of radiation therapy. These visits are part of RT standard of care. During each of these visits, patients will be asked about any cardiac or pulmonary changes, including any cardiac or pulmonary symptoms [i.e. shortness of breath, rapid heart beat, chest pain, and whether or not they have had any cardiac or pulmonary testing (i.e. ECG, echo, muga or PFTs)].
- 9.6 Early intervention termination
Not Applicable
- 9.7 Off study

Subjects will be considered off study after completing their one year (+/- 30 days) post RT follow-up visit. Subjects will also be considered off study if they chose to voluntarily withdraw from the study. They will be asked to be seen for a final end

of study follow-up that would include the same procedures as the follow-up appt. described in Section 9.5.

10. PHARMACOKINETIC STUDIES

Not applicable

11. DATA AND SAFETY MONITORING PLAN

11.1 Identification of the DSMB obligated for oversight responsibilities:

The Arizona Cancer Center Data and Safety Monitoring Board (DSMB) will provide ongoing oversight for this trial.

11.2 Identification of the entity obligated for routine monitoring duties:

Routine monitoring will be provided by the Quality Assurance/Quality Control (QA/QC) Program to ensure that the investigation is conducted according to protocol design and regulatory requirements.

11.3 Monitoring progress and data review process:

Routine monitoring of subject data will be conducted at least annually.

The first routine monitoring visit will include at a minimum:

- Informed consent – 50% of cases enrolled;
- Subject eligibility - 10% of cases, up to two subjects;
- Data review - 10% of cases, up to two subjects.

All subsequent monitoring visits will consist of randomly selected subject cases based on current enrollment and include continuing review of previously selected cases, as applicable.

A monitoring visit report and follow-up letter will be completed approximately two weeks after the routine monitoring visit; a copy will be maintained in the study file. A query/finding form or an electronic record will also be completed by the monitor to request additional source documentation, clarification, information or corrections to the CRF and/or regulatory records. The Clinical Research Coordinator or other applicable staff responsible for the study will be given a copy of this form, or will be notified of the electronic record for resolution of queries/findings. The query/finding form will be maintained with a copy of the visit report for follow-up at the next monitoring visit. Electronic records will be available in the institutional database or provided by the QA/QC Program staff.

The Principal Investigator will ensure the accuracy, completeness, legibility and timeliness of the data reported in the Case Report Form (CRF), or other acceptable data formats. Source documentation supporting the study data should indicate the subject's participation in the trial and should document the dates and details of study procedures, adverse events, and patient status.

Case report forms, which include the inclusion/exclusion criteria form, adverse event forms and serious adverse event forms *[other forms, depending on study]* should be completed via the institution database or other acceptable data

formats. Trials using paper CRFs will have the data entered with a black ball-point pen or typed. Corrections to the forms should not obscure the original entry and should be made by striking the incorrect information with a single line. Each strike should be accompanied by the initials of the corrector and the correction date. All subject forms and study files will be stored in a secure area limited to authorized staff.

Note: Routine monitoring of regulatory documents and test article will be conducted at least annually.

11.4 Process to implement study closure when significant risks or benefits are identified:

There are no plans for early study closure for this study, since the intervention used will actually reduce the side effects patients experience.

11.5 Description of adverse events and reporting procedures:

ADVERSE EVENTS

An adverse event (AE) is any untoward medical occurrence in a patient or clinical investigation subject administered a pharmaceutical product and that does not necessarily have a causal relationship with this treatment. An AE can therefore be any unfavorable and unintended sign, symptom, or disease temporally associated with the use of a medicinal (investigational) product, whether or not related to the medicinal (investigational) product.

Any and all adverse events will be recorded on the UMC adverse events record form and reviewed by the Principal Investigator.

All adverse events will be classified using either the MedDRA term or NCI Common Terminology Criteria for Adverse Events (CTCAE) version 3.0 or 4.0 and will address:

- Grade
- Relationship to study drug(not related, unlikely, possible, probable, definitely)
- Causality other than study drug (disease related, concomitant medication related, intercurrent illness, other)
- Date of onset, date of resolution
- Frequency of event (single, intermittent, continuous)
- Event outcome (resolved, ongoing, death)
- Action taken (none, held, dose reduced, discontinued, medication given)

SERIOUS ADVERSE EVENTS

A serious adverse event (SAE) is any untoward medical occurrence that at any dose:

- 1) Results in death;
- 2) Is life-threatening;
- 3) Requires in-patient hospitalization or prolongation of an existing hospital stay;
- 4) Results in disability persistent or significant disability/incapacity, or;
- 5) Is a congenital anomaly/birth defect.

Note: A SAE may also be an important medical event, in the view of the investigator that requires medical or surgical intervention to prevent one of the outcomes listed above.

All serious adverse events, regardless of attribution, and any deaths will be reported within 24 hours of notification of the event to the sponsor and DSMB Coordinator. All serious adverse events, regardless of attribution, and any deaths will be reported within 5 days of notification of the event to the University of Arizona Human Subjects Protection Program.

All serious adverse events will be processed by the DSMB Coordinator monthly for initial trend analysis and fully reviewed by the DSMB, every six months. The DSMB Coordinator will review the SAE reporting process to confirm reporting requirements are met.

11.6 Plan for assuring data accuracy and protocol compliance:

Routine study activity and safety information will be reported to the DSMB on an annual basis, or more frequently if requested. These reports will include:

- Study activity, cumulative and for the period under review;
- Safety (narrative description on non-serious and serious adverse events, protocol pre-determined early stopping rules for safety or treatment-emergent adverse events);
- Predetermined protocol early stopping rules for efficacy/futility;
- Status of study in relationship to stopping rules;
- Current dose level of study agent;
- Routine monitoring and protocol compliance (describe the monitoring process and identify the status of the monitoring);
- Comments;
- Attachments (AE data reviewed by the PI to compile the report, SAE letters and reports, results of any review(s), applicable correspondence with the IRB or other regulatory agencies

Data, safety and study progress will be reported to:

- Human Subjects Protection Program (IRB) at least annually;
- Sponsor (if applicable) at least annually.

Identification of the sponsor or funding agency, as applicable:

The PI will immediately notify, in writing, the funding agency, if applicable, any action resulting in a temporary or permanent suspension of the study.

A copy of this correspondence will also be forwarded to the DSMB and the SRC.

11.7 Process to implement study closure when significant risks or benefits are identified:

Not applicable.

12. ADDITIONAL SAFETY REPORTING

Serious adverse events will be reported to the Data Safety Monitoring Board as well as the institutional IRB within 24 hours of notification of the event to the PI.

Serious adverse events will be reported using the FDA MedWatch form to inform the DSMB, and using the F224 (Reportable Local New Information that is Potentially Problematic) form to inform the IRB.

13. QUALITY ASSURANCE MEASURES

Not applicable

14. RECIST CRITERIA

Not Applicable

15. REMOVAL OF SUBJECTS

Subjects have the right to withdraw from the study at any time and for any reason without prejudice to their future medical care by the physician or at the institution. If this occurs, the investigator, or designee, is to discuss with the subject the safe and appropriate processes for discontinuation from the investigational intervention.

The investigator or designee must document the change in status of the subject's participation in the study and as applicable, the level of follow up that is agreed to by the subject (i.e. agrees to follow up exams, adverse event review, phone contact, but not to further treatment and/or procedures).

Subject withdrawal of consent for a study indicates that the subject does not wish to receive further protocol required therapies or procedures, and the subject does not wish to, or is unable to continue further study participation. Subject data only up to the time when consent is withdrawn will be included in the analysis of the study.

16. STASTISITICAL CONSIDERATIONS

Statistical analysis will be performed in collaboration with [name], the Director of the University of Arizona Cancer Center Biometry Shared Service.

The primary endpoint of the study is the feasibility of the breath-hold technique for women treated with radiation for left-sided breast cancer in the prone position. Although it is expected that the number of women who are unable to master the breath-hold technique will be small, the proportion of women who cannot master the technique will be estimated with the appropriate exact 95% confidence interval.

The secondary endpoint is to evaluate the changes in the mean dose to the heart and lungs with prone breath hold. Each woman enrolled in the study will have two radiation plans generated in the prone position: one for the free-breathing scan and one for the breath-hold scan. The mean difference between the dosimetrically determined heart and lung radiation doses will be computed with the associated 95% confidence interval. A paired t test will be used to assess

whether the mean difference is statistically significant. The other secondary endpoints will be analyzed in a similar fashion.

Ten women will give 80% statistical power to detect a difference of 1 standard deviation unit in the mean dose between the two conditions. Note that since paired data will be generated, the number of women required is less than if two independent samples of women were to be used. Additionally, the percentage of women in which adding the breath-hold results in a lower cardiac and lung dose will be estimated with standard error of 16% or less. The estimated mean difference (and its standard error) will be used to generate the sample size required for a larger study to statically assess the benefit of adding the breath-hold in reducing the cardiac and lung radiation dose.

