2. STUDY DESIGN

2.1 Phase: This is a Pilot Study

2.2 Number of centers: One

This study will be performed by The University of Arizona Medical Center (UAMC) Radiation Oncology Department at both the University Campus Hospital and Orange Grove Clinic.

2.3 Number of subjects: Approximately 15

2.4 Subject participation time period:

Subjects will be enrolled in the study for 15 months, including screening time, treatment time, and follow-up at one year post radiation therapy.

Subjects enrolled in this study are undergoing treatment at UAMC Main Campus or Orange Grove Clinic as part of standard of care for the treatment of breast

cancer. Typical Radiation treatment schedule is between four and six weeks in length with treatments administered Monday through Friday.

SCHEMA

See Section 9.3

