If this study shows feasibility and potential for lowering cardiac and pulmonary dose for patients treated in the prone position with the addition of breath-hold then a larger randomized trial looking at optimal patient characteristics for this combined technique, further examining dose reductions using this experimental technique versus standard of care, and possible late toxicities, including cardiovascular and pulmonary, can be considered in the future.

4.2 Investigational Product:

Not applicable

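### The feasibility proportion has no stated time point or denominator, and read literally criterion 7 and section 9.4 push it toward zero

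*Combined protocol and SAP*

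**What the plan says.** Section 16 names the endpoint as follows (the quote stops one word before the sentence ends): "The primary endpoint of the study is the feasibility of the breath-hold technique for women treated with radiation for left-sided breast cancer in the prone". It expects few failures ("it is expected that the number of women who are unable to master the breath-hold technique will be small") and plans one analysis: "the proportion of women who cannot master the technique will be estimated with the appropriate exact 95% confidence interval". Mastery, the time at which it is judged and the women counted are not specified. The nearest description, in section 7.1, is a coaching instruction to hold for about 15 seconds inside a threshold bar. It gives no number of attempts and no pass mark. The planned size is "2.3 Number of subjects: Approximately 15".

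Four other places bear on who and what is counted:

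- **Section 6.1, criterion 7** (and section 1.4) admits only women who tolerate the prone breath hold; criterion 7 places this at the CT simulation.
- **Section 7.1** enrols women before that simulation. For those whose breath-hold plan gives the lower cardiac and lung doses, it says "inspiratory gating will be performed during each daily treatment".
- **Section 9.4** says "The intervention will be considered complete at the time" at which the plan exists.
- **Section 16** has two plans, one of them on the breath-hold scan, for every enrolled woman.

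The closing paragraph of the disease background in section 4 states how the result will be used: "If this study shows feasibility and potential for lowering cardiac and pulmonary dose", a larger randomised trial can be considered.

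**The concern.** A feasibility proportion is informative only if the women who cannot do the procedure remain in it. Here, a woman who is enrolled and then cannot hold her breath at simulation does not meet criterion 7. If she is treated as ineligible, the event that the primary endpoint is meant to count removes her from the count. Section 16 has the same tension within itself: it plans to estimate how many women fail, yet assumes that each enrolled woman has a breath-hold plan.

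The second gap is the treatment course. The endpoint concerns women treated with radiation, and those with a breath-hold plan repeat the hold at each weekday session, typically for four to six weeks (section 2.4). Section 16 names no measure of whether they complete the course that way, and section 9.4 places the end of the intervention before the first session. Nothing requires a woman who reverts to free breathing to be reported.

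Both gaps act in the same direction: the technique can look more feasible than it was. That matters because section 4 ties thinking about a larger trial to this result.

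**Working it through.** **1. The plan's own figures.** Inputs from section 16: 10 women, paired t test, difference of 1 SD, standard error of 16% or less. Alpha is not stated; two-sided 0.05 is assumed, and the SD is taken as that of the paired differences. With df = 9 and noncentrality 1 × √10 = 3.162, power is 0.803, against 80% stated. For a proportion, √(0.25/10) = 15.8%, within the stated 16%; at n = 15, √(0.25/15) = 12.9%. Both figures reproduce. Both concern the secondary dose outcomes. No figure is given for the primary endpoint.

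**2. Precision of the planned primary analysis.** Exact (Clopper-Pearson) 95% limits for x failures in n are the 0.025 quantile of Beta(x, n − x + 1) and the 0.975 quantile of Beta(x + 1, n − x). With x = 0 the lower limit is 0 and the upper limit is 1 − 0.025^(1/n). For n = 15 that is 1 − 0.025^(1/15) = 21.8%.

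| Failures | n = 15 | n = 10 |
|---|---|---|
| 0 | 0 to 21.8% | 0 to 30.8% |
| 1 | 0.2 to 31.9% | 0.3 to 44.5% |
| 2 | 1.7 to 40.5% | 2.5 to 55.6% |
| 3 | 4.3 to 48.1% | 6.7 to 65.2% |

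**3. Effect of criterion 7 on the denominator.** If f of n consented women fail at simulation, the proportion is f/n when they are kept. It is 0/(n − f) = 0 when they are removed as ineligible, whatever f is. Illustration with an assumed f = 3 and n = 15:

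- kept: 3/15 = 20%, CI 4.3% to 48.1%;
- removed: 0/12 = 0%, upper limit 1 − 0.025^(1/12) = 26.5%;
- removed and replaced up to 15 (the documents mention no replacement): 0/15 = 0%, upper limit 21.8%.

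The same women and the same scans give 20% or 0%, depending on a choice that the plan leaves open.

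**4. Sections 7.1 and 9.4 side by side.** Section 7.1 puts breath hold into each treatment session for one subset of women. Section 9.4 closes the intervention before any session. Section 16 does not say which period its proportion covers. Only women assigned a breath-hold plan can fail during the course, so a treatment-phase proportion has a smaller denominator than 15. If 10 women were assigned such a plan (an assumption), 0 failures would give 0 to 30.8% and 2 failures 2.5% to 55.6%.

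**The case against.** The strongest reply is that this is a pilot of about 15 women and that estimation with an exact interval is a legitimate aim. Section 4 says only that a larger trial can be considered, and it also asks for potential to lower dose, so it is not a go/no-go gate. This stands. The absence of a cutoff is a trade-off that the team may choose, provided it says so. For the same reason a reader should not infer that the pilot cannot speak to feasibility at all, or that nearly any result would pass: an interval is planned, and a high failure count would show in it.

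A reader might also infer from section 9.4 that the endpoint stops at plan generation, so that a woman who holds once and later reverts counts as a success. The documents do not say this. Section 9.4 ends the intervention, not expressly the endpoint; section 16 sets no time point; and section 7.1 has details of treatment collected. The data collection form listed in section 30 is not in the text reviewed, so recording of the technique delivered cannot be ruled out. What stands is that the time point is unstated and that 7.1 and 9.4 disagree.

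Finally, a reader might want one pass mark over both phases, such as at most 2 failures in 15. If each woman had the same failure rate, that rule would be met with probability 81.6%, 39.8% or 12.7% at true rates of 10%, 20% or 30% (assumed; none is in the documents). But whether a woman can fail in the second phase depends on a dosimetric result. Suppose 10% fail simulation and 20% of women with a breath-hold plan revert (also assumed). If 30% of those completing simulation receive that plan, overall failure is 0.10 + 0.90 × 0.30 × 0.20 = 15.4% and the rule is met 59% of the time. If 90% receive it, failure is 0.10 + 0.90 × 0.90 × 0.20 = 26.2% and the rule is met 21% of the time. A combined rule would therefore not measure feasibility alone.

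**Conclusion.** The point holds in a limited form. The primary proportion has no stated time point or denominator. Read literally, criterion 7 takes simulation failures out of it, and section 9.4 leaves the treatment course outside any stated analysis. The size of the first effect depends on how many women fail: 3 of 15 would move from 20% to 0%. The second cannot be sized from the documents, which give no rate of reversion to free breathing. Even with all 15 women counted and none failing, the interval reaches 21.8%, so the expected precision should be stated.

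The conclusion assumes that criterion 7 would be applied as written to women already enrolled. If the team intends to keep such women, the remedy is to say so. The documents do not show that the plan is confined to simulation, nor that a success threshold is obligatory.

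**What to change.** In section 16:

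1. Estimate simulation failure over all consented women who attempt the breath-hold simulation, keeping those who fail in the denominator, and say how failure is judged. Reconcile criterion 7 with sections 7.1 and 16, including the statement that each enrolled woman has two plans.
2. Report separately, among women assigned a breath-hold plan, the proportion who did not complete the course with breath hold, with the reason and an exact 95% CI. Reconcile section 9.4 with section 7.1.
3. State either that the aim is estimation only, with the expected precision at n = 15 (0 failures 0 to 21.8%; 2 failures 1.7% to 40.5%; 3 failures 4.3% to 48.1%), or a level for the simulation failure proportion that the team fixes in advance.

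The cost is wording in sections 6.1, 7.1, 9.4 and 16, slightly more analysis, and a check that the data collection form records the technique delivered. The feasibility figure will probably look less favourable. No woman's treatment changes.

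### Does sizing the larger study from the paired mean difference and its standard error leave a later randomized trial underpowered?

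*Combined protocol and SAP*

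**What the plan says.** Section 16 gives each woman two prone plans, one free-breathing and one breath-hold, and compares doses by the mean within-woman difference, its 95% confidence interval and a paired t test. The power statement is "Ten women will give 80% statistical power to detect a difference of 1 standard deviation unit in the mean dose between the two conditions". It adds that, because the data are paired, "the number of women required is less than if two independent samples of women were to be used". The section then looks ahead: "The estimated mean difference (and its standard error) will be used to generate the sample size required for a larger study", a study meant to "assess the benefit of adding the breath-hold in reducing the cardiac and lung radiation dose". It names no design, formula, significance level or power for that study.

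The last paragraph of the Background, just before the Investigational Product heading, makes a different forward reference. If the pilot shows feasibility and potential for lower dose, "then a larger randomized trial looking at optimal patient characteristics for this combined technique" might follow. That trial would also compare dose with usual care and look at late toxicity, but the paragraph says only that it "can be considered in the future".

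No section promises to report the SD of dose under each condition or the correlation between a woman's two plans.

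**The concern.** Read together, the two places seem to size a randomized trial from a paired quantity. The standard error of the paired mean difference carries only the SD of the within-woman difference. Two randomized arms compared on dose, without adjustment, vary by the between-woman SD instead. When a woman's two plans are strongly correlated, the first SD is much smaller than the second, and a trial sized on it would be too small.

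Sizing a larger study is a stated use of this pilot, so a wrong input could waste that study. The estimates would also come from only about 15 women (section 2.3), with no stated allowance for their imprecision.

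**Working it through.** **Inputs.** From section 16: n = 10, 80% power, a difference of 1 SD, paired t test. Assumed: two-sided 5% (section 16 uses 95% intervals but states no alpha); 1 SD read as the SD of the within-woman difference, SDd; equal SDs under the two conditions. The correlation rho between a woman's two plans is not in the documents, so it is varied.

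**The plan's own figure.** Paired t test, noncentral t with n − 1 degrees of freedom and noncentrality sqrt(n) × 1: n = 9 gives 74.8%, n = 10 gives 80.3%. Ten is the smallest number that reaches 80%. The figure is right.

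**What is carried forward.** SDd = standard error × sqrt(n). With sigma the between-woman SD, SDd = sigma × sqrt(2(1 − rho)). One number cannot give both sigma and rho, so the algebra behind the concern is correct.

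**Three possible larger studies**, each with a true difference of 1 SDd:

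1. *Each woman planned both ways again.* The relevant SD is SDd. The mean difference and its standard error are the right inputs.

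2. *Two randomized arms, unadjusted, sized by putting SDd into the two-sample formula.* This gives 17 per arm (16 per arm gives 78.1%, 17 gives 80.7%). The true standardized difference is sqrt(2(1 − rho)).

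3. *Two randomized arms, with the free-breathing planned dose as covariate, sized the same way.* Residual variance = sigma² × (1 − rho²). Since sigma² = SDd² / (2(1 − rho)), this equals SDd² × (1 + rho)/2, which never exceeds SDd². The standardized difference is 1/sqrt((1 + rho)/2), at least 1.

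| rho | Standardized difference, unadjusted | Needed per arm, unadjusted | Power at 17 per arm, unadjusted | Standardized difference, adjusted | Power at 17 per arm, adjusted |
|---|---|---|---|---|---|
| 0.25 | 1.22 | 12 | 93% | 1.26 | 95% |
| 0.5 | 1.00 | 17 | 81% | 1.15 | 90% |
| 0.7 | 0.77 | 28 | 59% | 1.08 | 87% |
| 0.8 | 0.63 | 41 | 43% | 1.05 | 85% |
| 0.9 | 0.45 | 80 | 24% | 1.03 | 83% |

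All power figures use 32 degrees of freedom; removing one for the covariate changes the last column by less than 0.1 percentage point.

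The shortfall therefore appears only in case 2 with rho above 0.5. Below 0.5 the same shortcut gives too many women. In case 3 it is sufficient at every rho; knowing rho would only trim the number, for example from 17 to 16 per arm at rho 0.8.

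**Imprecision.** The 95% limits for an SD are sqrt((n − 1)/chi-square quantile) times the estimate: 0.73 to 1.58 for 15 women, 0.69 to 1.83 for 10. Squared, the required number can be 0.54 to 2.5 times the calculated one (15 women) or 0.47 to 3.3 times (10 women). This holds for any pilot of this size.

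**The case for a change.** The strongest case for a change is this. The only larger study described anywhere is the randomized one, and no section says the next study will be paired. The plan recognises that independent samples need more women, yet names only the paired quantities as inputs. A milder misuse was taken above; a worse one exists. If the paired sample size were used as the total of a randomized trial, a difference of 0.5 SDd would give 34 women, 17 per arm, with 52% power at rho 0, 29% at 0.5 and 15% at 0.8. Even for a repeat paired study, sizing on the point estimates of a 15-woman pilot left true power below 80% in about 45% of simulated pilots. The remedy would cost one sentence.

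The algebra and figures stand, and it is true that nobody promises to report the between-woman SD or the correlation. What does not stand is that the plan, followed as written, leads there. Treating the two larger studies as one is an inference: section 16 names no design, and the Background offers a randomized trial only as something to consider. The severe figures also need dose to be what sizes the trial, the arms to be compared without the free-breathing dose (a plan section 7.1 calls standard of care), a paired SD or sample size to be used for a two-arm comparison, and, in the two-sample-formula version, rho above 0.5. Nothing in the documents states any of these. A statistician who has written that pairing reduces the number of women is unlikely to make that substitution.

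The imprecision point is fair but general. The planned 95% interval for the mean difference will show much of it, and which upper limit to plan on is a convention best chosen when the next study is designed.

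**Conclusion.** No change is needed. What is missing is a description of how a study not yet designed would be sized, and that gap can be filled later at no loss. Both planned doses are obtained for every woman, so the SD under each condition, the correlation and SDd can all be computed from the pilot data when a design is chosen, and section 16 already has the analysis done with the cancer center's Biometry Shared Service.

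Nothing in the pilot moves: its sample size (80.3% power at ten women), the feasibility estimate, the paired tests and the confidence intervals are unaffected. The possible harm, power of 59%, 43% or 24% at rho 0.7, 0.8 or 0.9, belongs to one unadjusted analysis of a trial the plan does not commit to, sized by a formula it does not give. Under the other two designs the paired inputs are correct or sufficient. This conclusion assumes equal SDs, two-sided 5% tests, a true difference of 1 SDd and, for the adjusted analysis, a free-breathing planned dose for every woman in both arms. Stating that 1 SD means the SD of the within-woman difference would be a courtesy to readers, not a correction.
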